## 21.0 Provisions to Monitor the Data to Ensure the Safety of Subjects\*

- N/A:** This study is not enrolling subjects, or is limited to records review procedures only. This section does not apply.

**NOTE: Minimal risk studies may be required to monitor subject safety if the research procedures include procedures that present unique risks to subjects that require monitoring. Some examples include: exercising to exertion, or instruments that elicit suicidality or substance abuse behavior. In such cases, N/A is not an acceptable response.**

*21.1 Describe the plan to periodically evaluate the data collected regarding both harms and benefits to determine whether subjects remain safe.*

Response: This study is of minimal risk. Patients' treatment notes will be reviewed after each visit to ensure safety per SOC.

*21.2 Describe what data are reviewed, including safety data, untoward events, and efficacy data.*

Response: Efficacy data: canine retraction amount and monthly rate

*21.3 Describe any safety endpoints.*

Response: NA

*21.4 Describe how the safety information will be collected (e.g., with case report forms, at study visits, by telephone calls with participants).*

Response: NA

*21.5 Describe the frequency of safety data collection.*

Response: NA

*21.6 Describe who will review the safety data.*

Response: NA

*21.7 Describe the frequency or periodicity of review of cumulative safety data.*

Response: NA

*21.8 Describe the statistical tests for analyzing the safety data to determine whether harm is occurring.*

Response: NA

*21.9 Describe any conditions that trigger an immediate suspension of the research.*

**Response:** NA

## **22.0      Withdrawal of Subjects\***

**N/A:** This study is not enrolling subjects. This section does not apply.

*22.1 Describe anticipated circumstances under which subjects may be withdrawn from the research without their consent.*

**Response:** If the subjects:

- Develop any indication of root resorption
- Develop any periodontal issues during the course of the study
- Develop any health-related issues during the study
- Voluntarily want to leave the study or cease treatment
- Do not come regularly as needed for the study

*22.2 Describe any procedures for orderly termination.*

*NOTE: Examples may include return of study drug, exit interview with clinician. Include whether additional follow up is recommended for safety reasons for physical or emotional health.*

**Response:** The subjects may withdraw their consent and discontinue their participation at any time. At which point, all collected data of the subject will be destroyed and discarded accordingly.

*22.3 Describe procedures that will be followed when subjects withdraw from the research, including retention of already collected data, and partial withdrawal from procedures with continued data collection, as applicable.*

**Response:** If subjects withdraw from the research, their data will not be used in the research study as the data will not be complete. It will be destroyed and discarded accordingly. The IRB correspondence and signed consent forms from withdrawn subjects will be maintained for 3 years.

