**Response:**

- Adolescents of both gender (12-17Y11M),
- undergoing orthodontics treatment with full fixed appliances,
- good oral hygiene / health,
- with bilateral spaces  $3 \geq$  mm distal to the maxillary permanent canines,
- normal and hypodivergent growth patterns.

9.2 *Describe the criteria that define who will be **excluded** from your final study sample.*

*NOTE: This may be done in bullet point fashion.*

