**Response:**

- Systemic diseases or syndromes,
- abnormalities in tooth shape and/or size,
- previous orthodontic treatment,
- medications that can affect the outcome of the study,

- craniofacial anomalies,
- periodontal disease or attachment loss,
- significant root resorption prior to or during the study (more than 1/3rd root length).
- Patients with known allergy to nickel

9.3 *Indicate specifically whether you will include any of the following special populations in your study using the checkboxes below.*

**NOTE: Members of special populations may not be targeted for enrollment in your study unless you indicate this in your inclusion criteria.**

Response:

- Adults unable to consent
- Individuals who are not yet adults (infants, children, teenagers)
- Pregnant women
- Prisoners

9.4 *Indicate whether you will include non-English speaking individuals in your study. Provide justification if you will exclude non-English speaking individuals.*

*In order to meet one of the primary ethical principles of equitable selection of subjects, non-English speaking individuals may **not** be routinely excluded from research as a matter of convenience.*

*In cases where the research is of therapeutic intent or is designed to investigate areas that would necessarily require certain populations who may not speak English, the researcher is required to make efforts to recruit and include non-English speaking individuals. However, there are studies in which it would be reasonable to limit subjects to those who speak English. Some examples include pilot studies, small unfunded studies with validated instruments not available in other languages, studies with numerous questionnaires, and some non-therapeutic studies which offer no direct benefit.*

**Response:** We will not be including Non-English-speaking subjects. All of the treatment is available as Standard of Care and no potential benefits would be inequitably withheld from Non-English-speakers.

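### Sections 9.2 and 22.3 can drop a randomised patient, even one with complete scans, because of an event the treatment may have caused

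*Combined protocol and SAP*

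**What the plan says.** Four parts of the protocol bear on this.

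- **Section 9.2 (exclusion).** The form asks who is excluded "from your final study sample". The list includes "significant root resorption prior to or during the study", with a threshold of more than one third of root length.
- **Section 22.1 (withdrawal without the subject's consent).** The circumstances include "Develop any indication of root resorption", with no threshold, and any periodontal or health-related issue that develops on study. Voluntary departure is in the same list.
- **Sections 22.2 and 22.3 (what happens to the data).** Under 22.2, when a subject withdraws consent, "all collected data of the subject will be destroyed and discarded accordingly". Under 22.3: "If subjects withdraw from the research, their data will not be used in the research study as the data will not be complete". Those data are destroyed. It ends: "The IRB correspondence and signed consent forms from withdrawn subjects will be maintained for 3 years".
- **Sections 13.1, 20.1 and 20.2 (schedule, analysis and sample size).** Scans are taken up to T4, and radiographs are listed at T4. The comparison is a paired t-test. The sample is 16, for 80% power at 0.05 to detect 0.5 mm. No SD, withdrawal rate, analysis set or missing-data method is given.

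**The concern.** Section 23.2 names root resorption among the potential risks of the forces applied. A rule that removes patients who develop it therefore selects on something the treatment may have caused, after the sides have been randomised. The patients left in the analysis would be those in whom no such problem was found.

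Two things are at stake. First, each removed patient costs a pair, and 8.1 enrols exactly the 16 that 20.2 relies on. Second, a removed patient's side difference could differ from the others', which is harder to examine if the study data have been destroyed.

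The rules also do not fit together. Section 22.1 acts on any sign of resorption, while 9.2 acts above one third of root length. The reason given in 22.3 is that the data are incomplete, but resorption seen on the T4 radiograph concerns a patient whose scans may all be in hand.

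**Working it through.** **1. What the text allows**

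| Rule | Trigger | Can act after randomisation? | Effect on data |
|---|---|---|---|
| 9.2 | Resorption over one third of root length, before or during the study | Yes, through the words 'or during' | Out of the final sample |
| 22.1 with 22.3 | Any resorption, periodontal or health issue | Yes | Not used and destroyed, if 22.3 covers investigator withdrawal |
| 22.2 | Subject withdraws consent | Yes | Destroyed |

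The 9.2 route does not depend on how 22.3 is read. The 22.1 route does.

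**2. The plan's sample size**

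Inputs from 20.1 and 20.2: n = 16, difference 0.5 mm, power 80%, alpha 0.05, paired t-test. The SD is not given, so 16 cannot be reproduced independently. Assuming a two-sided test, I solved for the SD of within-patient differences that gives exactly 80% power (noncentral t, 15 df, noncentrality = 0.5 × √16 / SD). The result is SD = 0.667 mm. The standard error is 0.667/√16 = 0.167 mm.

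**3. Loss of pairs**

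Same SD, with the retained patients' mean difference at 0.5 mm:

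| Pairs analysed | Power |
|---|---|
| 16 | 80.0% |
| 15 | 77.0% |
| 14 | 73.7% |

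A one-sided test would imply SD = 0.767 mm and give 77.5% and 74.7% with 15 and 14 pairs, which is much the same.

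No rate is given for the triggers. If each patient had a 5% chance of meeting one, the chance of losing at least one pair is 1 − 0.95^16 = 56%. At 10% it is 1 − 0.90^16 = 81%. Both rates are assumptions.

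**4. Possible shift in the estimate**

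If k of 16 patients are removed and their mean side difference is d mm away from that of the rest, the retained mean is off by k × d/16. As an illustration, take d = 0.5 mm, the whole target difference:

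- k = 1: 0.5/16 = 0.031 mm, or 6% of 0.5 mm and 0.031/0.167 = 0.19 standard errors.
- k = 2: 1.0/16 = 0.0625 mm, or 12.5% of 0.5 mm and 0.0625/0.167 = 0.37 standard errors.

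The sign of d is unknown, so the shift could go either way. It would also move power away from the table above. If the mean over all 16 is 0.5 mm, the retained mean is 0.469 or 0.531 mm at k = 1, giving power of 72% or 82%. At k = 2 it is 0.4375 or 0.5625 mm, giving 62% or 83%. The 77% and 74% therefore hold only when the retained mean is 0.5 mm.

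**The case against.** The strongest reply is that 22.3 speaks of subjects who withdraw, while 22.1 only says that subjects may be withdrawn. Sections 22.2 and 22.3 answer separate prompts on a form, so the repeated destruction sentence proves little, and the phrase about withdrawn subjects stands in a sentence on paperwork. This stands in part: 22.3 is ambiguous, and a reader might wrongly infer that it plainly orders destruction after investigator withdrawal. It can be read so, because 22.1 puts both kinds of departure in one list and no other section gives a data rule for the investigator's decision. Section 9.2 is unaffected by the ambiguity.

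Three further points stand:

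- **The design limits bias.** In a split-mouth trial both wires lose the same patients. The documents give no reason why patients with resorption should have a different side difference. A reader might infer that the comparison is biased in a known direction, and the documents do not support that.
- **Loss may not be total.** Section 13.4 names clinical systems that hold models, images and treatment history, and nothing says those records are destroyed. It would be too strong to say that the removed patients could never be examined.
- **Harms are watched.** Section 21.1 says "treatment notes will be reviewed after each visit to ensure safety per SOC", and 23.2 plans checks and recorded concerns at visits. Section 21.2 answers only "Efficacy data: canine retraction amount and monthly rate", and 21.3 to 21.9 are marked not applicable. A reader might infer that harms go unmonitored, but 21.1 and 23.2 say otherwise. The lack of a stated study-level listing is missing detail in a study declared minimal risk, and the data spreadsheet is not in the documents.

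It is also fair to say that any dropout lowers power when there is no allowance. What is particular here is that these rules discard patients whose data could have been kept.

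**Conclusion.** The point holds in a limited form. Section 9.2 as written removes some patients on a finding that can arise after randomisation. Sections 22.1 and 22.3 can be read to do the same at a lower threshold and to destroy the data. Either can discard a patient with complete scans, contrary to the reason that 22.3 itself gives.

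The size is moderate. One or two removals take power from 80% to about 77% or 74%, assuming a two-sided paired t-test, an SD of 0.667 mm solved from the plan's own figures, and a retained mean of 0.5 mm. A shift of 0.03 to 0.06 mm needs the removed patients to differ by the full 0.5 mm, and its direction is unknown. How often the triggers would occur is not given. This does not undermine the trial, but the wording should be changed because the loss is avoidable at little cost.

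**What to change.** 1. **Section 9.2.** Delete the words 'or during', so that resorption is a baseline exclusion only. Clinical stopping for resorption stays in 22.1, unchanged.
2. **Section 22.3.** Limit destruction of data to withdrawal of consent, as in 22.2. For withdrawal by the investigator:
   - keep the scans already taken;
   - include every patient with a T4 scan in the primary paired analysis;
   - use patients withdrawn earlier in a sensitivity analysis only, as the side difference in rate up to the last scan, because rates over unequal follow-up do not belong in an unweighted primary paired t-test;
   - report the number of withdrawals and the reason for each, with the side where it applies.

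A short descriptive listing of harms in 21.2 would be a reasonable addition, but it is optional and the point does not depend on it.

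**Cost.** Small wording changes in two sections, a withdrawal reason and side in the data sheet if they are not already there, and possibly a sentence in the parental consent and the assent forms on keeping data after investigator withdrawal. No visit or radiograph is added. Data from early withdrawals will be noisier, which is a further reason to keep them to the sensitivity analysis.

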## **23.0      Risks to Subjects\***

*23.1 List the reasonably foreseeable risks, discomforts, hazards, or inconveniences to the subjects related to their participation in the research. Consider physical, psychological, social, legal, and economic risks. Include a description of the probability, magnitude, duration, and reversibility of the risks.*

*NOTE: Breach of confidentiality is always a risk for identifiable subject data.*

**Response:** Breach of confidentiality is a risk to participating in this study. Since this is a clinical research study, which will be utilizing orthodontic techniques and mechanics to achieve orthodontic treatment, we will have inherent risks which are routine in orthodontic treatment. These risks will be explained to the patient as part of the Standard of Care protocol.

*23.2 Describe procedures performed to lessen the probability or magnitude of risks, including procedures being performed to monitor subjects for safety.*

**Response:** Procedures performed to mitigate risk of confidentiality breach are described in the Confidentiality section.

To reduce the probability / magnitude of risks in the standard clinical procedures, safety measures will be implemented per SOC protocol.

- All biomechanical orthodontic forces will be standardized and delivered within standard of care parameters, keeping forces continuous but light to reduce any potential risk of; pain, discomfort, and root resorption.
- Patients will be given appropriate oral hygiene tools (floss threaders, proxy brushes, tooth brushes, plaque disclosing tablets) and instruction prior to starting orthodontic treatment. This will ensure that each patient is aware of the hygiene required during treatment. This will also reduce the risk of white spot lesions, periodontal issues, and halitosis. Reduced inflammation will also provide more comfort to the patient during treatment.
- To reduce risk of discomfort and abrasion, patients will be given orthodontic wax to place on brackets or wires that give them any discomfort. Patient's wires will be trimmed accordingly and patient will be asked prior to leaving if there is anything bothering them to reduce discomfort.
- Each adjustment visit patients will be assessed clinically extra orally and intraorally to evaluate any changes and look for pathology, inflammation, abrasions, and any tooth damage (white spot lesions, fractures, caries). Tissues will be assessed for inflammation and erythema. Radiography will be taken to assess the root anatomy, alveolar bone level, TMJ anatomy and screen for any pathology)
- Patients will be able to communicate the research examiner if there are any issues between adjustment visits (discomfort, broken appliance, pain, difficulty chewing/eating, psychological issues). They will be either seen for an emergency visit to address the concern or guided via tele-dentistry communication to resolve the issue if possible.
- Patients will have their medical and dental history updated at every visit to ensure that all appropriate changes in their health are on record. They will be asked about any concerns or issues they are having, which will be recorded and addressed accordingly.

- Regarding patients who have or develop an allergic reaction to nickel, there will be appropriate changes made to their treatment to prevent the allergy.

**23.3** *If applicable, indicate which procedures may have risks to the subjects that are currently unforeseeable.*

**Response:** This current study is minimal risk. The general risk is a broken appliance, which is a risk inherent to standard clinical care for these patients.

**23.4** *If applicable, indicate which research procedures may have risks to an embryo or fetus should the subject be or become pregnant.*

Response: N/A

**23.5** *If applicable, describe risks to others who are not subjects.*

**Response:** Current risk of COVID-19 infection, otherwise there is risks to others who are not subjects.

## **24.0 Potential Benefits to Subjects\***

**24.1** *Describe the potential benefits that individual subjects may experience by taking part in the research. Include the probability, magnitude, and duration of the potential benefits. Indicate if there is no direct benefit.*

*NOTE: Compensation **cannot** be stated as a benefit.*

**Response:** There are no direct benefits to subjects on this study, they are being randomized to standard treatments that are available to any patient outside of the research context.

## **25.0 Compensation for Research-Related Injury**

**N/A:** The research procedures for this study do not present risk of research related injury (e.g. survey studies, records review studies). This section does not apply.

**25.1** *If the research procedures carry a risk of research related injury, describe the available compensation to subjects in the event that such injury should occur.*

**Response:** This study is of minimal risk, and there is no additional anticipated risk for participating in this study

**25.2** *Provide a copy of contract language, if any, relevant to compensation for research related injury.*

*NOTE : If the contract is not yet approved at the time of this submission, submit the current version here. If the contract is later approved with **different language regarding research related injury**, you must modify your response here and submit an amendment to the IRB for review and approval.*

Response: NA, this study is not sponsored.

## 26.0 Economic Burden to Subjects

26.1 *Describe any costs that subjects may be responsible for because of participation in the research.*

*NOTE: Some examples include transportation or parking.*

**Response:** Patients will be required to cover the following costs as part of their regular care:

- Standard clinical fees associated with comprehensive orthodontic treatment
- There will not be additional cost to receiving the GUMMETAL wire.

**N/A:** This study is not enrolling subjects, or is limited to records review procedures only. This section does not apply.

## 27.0 Compensation for Participation

27.1 *Describe the amount and timing of any compensation to subjects, including monetary, course credit, or gift card compensation.*

Response:

**N/A:** This study is not enrolling subjects, or is limited to records review procedures only. This section does not apply.

**N/A:** There is no compensation for participation. This section does not apply.

## 28.0 Consent Process

28.1 *Indicate whether you will be obtaining consent.*

*NOTE: This does not refer to consent documentation, but rather whether you will be obtaining permission from subjects to participate in a research study. Consent documentation is addressed in Section 27.0.*

**Yes** (*If yes, Provide responses to each question in this Section*)

**No** (*If no, Skip to Section 27.0*)

28.2 *Describe where the consent process will take place. Include steps to maximize subjects' privacy.*

**Response:** Consent will take place at the University at Buffalo School of Dental Medicine in the Orthodontic Department. Specifically, this will take place in the privacy of a faculty office which will be completely closed and private. Patients will be able to ask their questions and concerns with absolute privacy.

*28.3 Describe how you will ensure that subjects are provided with a sufficient period of time to consider taking part in the research study.*

*NOTE: It is always a requirement that a prospective subject is given sufficient time to have their questions answered and consider their participation. See “SOP: Informed Consent Process for Research (HRP-090)” Sections 5.5 and 5.6.*

**Response:** Patients will be allotted appropriate time to discuss amongst themselves and appropriate parent / guardians with or without the research examiner present, whichever they prefer. If subjects need more time to think and discuss outside of the clinic and come back at a later time to make their decision to participate this is acceptable. Patients can take as long as needed to make their decision and voice their concerns, there will be no time restriction or pressure from the research team.

*28.4 Describe any process to ensure ongoing consent, defined as a subject’s willingness to continue participation for the duration of the research study.*

**Response:** Patients will be asked at every visit if they wish to continue in their current research study. Patient will have full autonomy to withdraw or continue. There will be appropriate documentation that will be signed by the patient to ensure consent was given.

*28.5 Indicate whether you will be following “SOP: Informed Consent Process for Research (HRP-090).” Pay particular attention to Sections 5.4-5.9. If not, or if there are any exceptions or additional details to what is covered in the SOP, describe:*

- *The role of the individuals listed in the application who are involved in the consent process*
- *The time that will be devoted to the consent discussion*
- *Steps that will be taken to minimize the possibility of coercion or undue influence*
- *Steps that will be taken to ensure the subjects’ understanding*

**Response:**

We have reviewed and will be following “SOP: Informed Consent Process for Research (HRP-090).”

### ***Non-English Speaking Subjects***

**N/A:** This study will not enroll Non-English speaking subjects.  
(*Skip to Section 26.8*)

**28.6** *Indicate which language(s) other than English are likely to be spoken/understood by your prospective study population or their legally authorized representatives.*

*NOTE: The response to this Section should correspond with your response to Section 6.4 of this protocol.*

**Response:** N/A

**28.7** *If subjects who do not speak English will be enrolled, describe the process to ensure that the oral and written information provided to those subjects will be in that language, how you will ensure that subjects are provided with a sufficient period of time to consider taking part in the research study, and any process to ensure ongoing consent. Indicate the language that will be used by those obtaining consent.*

*NOTE: Guidance is provided on “SOP: Informed Consent Process for Research (HRP-090).”*

**Response:** N/A

